9.2. Duration of the Study and Subject Participation

Participation will begin at the signing of the ICF/obtaining written assent. No more than 30 days should pass between signing of the ICF/obtaining written assent and the administration of study drug. The time from study drug administration till the end of participation is 30 ± 3 days. Therefore, subjects may participate in the study for up to 63 days.

9.3. Data Safety Monitoring Board

If Pacira, the investigator, or officials from regulatory authorities discover conditions during the study that indicate that the study or study site should be terminated, this action may be taken after Pacira has consulted with appropriate regulatory authorities and notified the investigator(s). A Data Safety Monitoring Board (DSMB) will be set up to monitor the safety and dosing data on an ongoing basis for all treatment groups, with additional expedited DSMB review conducted as necessary.

9.4. Discussion of Study Design

This study is designed to formulate specific guidance regarding dose for the safe administration of EXPAREL in the pediatric population aged 6 to less than 17 years. EXPAREL doses recommended for adults are expressed as absolute values or ranges, whereas doses for pediatric subjects will be based on body weight, consistent with general prescription standards used in pediatric practice.

A population PK modeling of the infiltration studies in adults and simulations to support child/adolescent dosing was performed. Predicted values generated by the final model adequately described observed bupivacaine concentrations following administration of EXPAREL. According to this model, a dose of 4 mg/kg would produce bupivacaine concentrations in pediatric patients aged 6 to less than 17 years analogous to those observed in the adult infiltration studies.

In addition, the available data from The Cleveland Clinic (as discussed in Section 7.5) shows that the average dose among 375 pediatric patients was 4.1 ± 1.8 mg/kg, with no significant AEs attributed to EXPAREL use. This study is designed to further characterize the PK profile and to confirm the safety of the 4 mg/kg dose of EXPAREL.

A population PK sampling scheme will be used to limit the number of blood draws. A total of 8 blood samples will be collected from each subject at the specific post-dose time windows shown in Table 2 for the determination of bupivacaine plasma concentrations.

10. STUDY POPULATION

Subjects must meet all eligibility criteria to be enrolled in this study.

10.1. Inclusion Criteria

Subjects eligible for study entry must meet all of the following criteria:

- 1. Subjects whose parent(s) or guardian(s) has/have signed and dated the ICF for the subject to participate in the study, and subjects who have provided written assent to participate in the study (if capable).
- 2. American Society of Anesthesiologists (ASA) Class 1-3.
- 3. Male or female subjects 6 to less than 17 years of age on the day of surgery.
- 4. Body mass index (BMI) at screening within the 5th to 95th percentile for age and sex (see Appendix 5).
- 5. A negative pregnancy test for female subjects of childbearing potential must be available prior to the start of surgery. The pregnancy test must be conducted in the preoperative holding area according to the study site's standard of care.
- 6. Subjects and their parent(s)/guardian(s) must be able to speak, read, and understand the language of the ICF and any instruments used for collecting subject-reported outcomes to enable accurate and appropriate responses to study assessments, and provide informed consent/assent.
- 7. Subjects must be able to adhere to the study visit schedule and complete all study assessments.

10.2. Exclusion Criteria

A subject will not be eligible for the study if any of the following criteria is met:

- 1. Currently pregnant, breastfeeding, or planning to become pregnant during the study or within 1 month after study drug administration.
- 2. History of hypersensitivity or idiosyncratic reactions to amide-type local anesthetics or to opioid medication.
- 3. Contraindication to bupivacaine HCl or other amide-type local anesthetics or to opioid medication.
- 4. Administration of EXPAREL or bupivacaine HCl within 30 days prior to study drug administration.
- 5. Subjects with coagulopathies or immunodeficiency disorders.
- 6. History of, suspected, or known addiction to or abuse of drugs or alcohol within the past 2 years.

- 7. Clinically significant medical or psychiatric disease that, in the opinion of the investigator, indicates an increased vulnerability to study drugs and/or procedures.
- 8. Administration of an investigational drug within 30 days or 5 elimination half-lives of such investigational drug, whichever is longer, prior to study drug administration, or planned administration of another investigational product or procedure during the subject's participation in this study.

In addition, the subject will be ineligible to receive study drug if he or she meets the following criterion during surgery:

 Any clinically significant event or condition uncovered during the surgery (e.g., excessive bleeding, acute sepsis) that might render the subject medically unstable or complicate the subject's postoperative course.

10.3. Removal of Subjects from Therapy or Assessment

Every reasonable effort should be made to maintain subject compliance and participation in the study. Subjects who withdraw from the study after receiving study drug should undergo safety assessments till the end of the study (Day 30).

If a subject who withdraws from the study has an ongoing AE, every effort must be made to follow such events until satisfactory resolution is obtained, or further follow-up is otherwise no longer warranted.

10.3.1. Withdrawal Secondary to Adverse Events

If a subject experiences an AE that renders him or her incapable of continuing with the remaining study assessments, then he or she will be discontinued from further participation in the study. A final evaluation visit should be performed so that the subject's study participation can be terminated in a safe and orderly manner. Otherwise, the subject's parent or guardian will be instructed to notify the study personnel of any abnormalities during the intervals between study visits and to come to the study site if medical evaluation is needed and the urgency of the situation permits. Any subject exhibiting undesirable AEs will receive appropriate treatment at the discretion of the investigator.

This study involves a single administration of the study drug; therefore, subjects should not be terminated from the ongoing study assessments as long as they are willing and able to continue with the follow-up schedule according to the protocol. For emergencies and other unscheduled visits to a medical facility other than the study site, medical records will be obtained by the investigator.

10.3.2. Voluntary or Study Investigator Withdrawal

Subjects (or their parent or guardian) are free to discontinue participation in the study at any time, without prejudice to future treatment. Nevertheless, subjects will be encouraged to complete at least the study safety assessments. In addition, a subject may be discontinued from

the study if he or she refuses to comply with study procedures. Reasons for discontinuation from the study will be recorded.

If a subject is discontinued by the investigator or voluntarily withdraws from the study after receiving study drug, the subject will be asked to complete a final evaluation so that he or she can be withdrawn in a safe and orderly manner. In the final evaluation, vital signs (temperature, resting heart rate, respiratory rate, oxygen saturation, and blood pressure) and any changes in the subject's health status will be recorded.

After termination from the study, the subject may be followed for safety including monitoring of AEs till Day 30.

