12.4. Safety Endpoints

The following safety endpoints will be assessed based on the safety measurements conducted at the specified time points:

- Change from baseline in vital signs (temperature, resting heart rate, respiratory rate, oxygen saturation, and blood pressure).
- Summary of neurological assessments (proportion of subjects who are oriented, and proportion of subjects who have any neurologic events). Note: Events identified during the neurologic assessment should be recorded as AEs.
- Change from baseline in clinical laboratory data.
- Incidence of TEAEs and SAEs till Day 30.

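### The protocol is inconsistent on whether dosed children who leave the study are followed to Day 30, so new events after the final evaluation may go uncollected

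*Protocol*

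**What the plan says.** Protocol Section 10.3 gives the general rule: "Subjects who withdraw from the study after receiving study drug should undergo safety assessments till the end of the study (Day 30"). For a child who withdraws with an AE still ongoing it goes further: "every effort must be made to follow such events until satisfactory resolution is obtained", or until follow-up is no longer warranted.

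Section 10.3.1 deals with a child whose AE leaves him or her unable to go on with the remaining assessments. Such a child, it says, "then he or she will be discontinued from further participation in the study". The only contact it then names is this: "A final evaluation visit should be performed". It does not mention Day 30. Its second paragraph points out that the drug is given once and adds that "subjects should not be terminated from the ongoing study assessments as long as they are willing and able to continue".

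Section 10.3.2 covers children who leave voluntarily or are withdrawn by the investigator. They are encouraged to complete the safety assessments and asked for a final evaluation, which records vital signs and changes in health. After that, "After termination from the study, the subject may be followed for safety including monitoring of AEs till Day 30".

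Three other sections state no exception for children who have left. Section 9.1 plans a Day 30 visit for AE assessment for every dosed subject. Section 14.1.2 requires all AEs up to Day 30 to be recorded. Section 14.2.2 requires any SAE or death through Day 30 to be reported.

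The endpoint in Section 12.4 is "Incidence of TEAEs and SAEs till Day 30".

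**The concern.** The endpoint needs the same 30 days of observation in every dosed child. If a site treats follow-up after withdrawal as optional, or as finished at a final visit, an event that starts later reaches the database only if the site happens to hear of it.

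The SAP would not correct for this. Section 6.1 bases percentages on everyone in the treatment group or group within the analysis population, and the TEAE tables in Section 6.8.4 are crude subject counts. A child seen for a few days therefore counts as event-free for the rest of the period. Section 4 of the SAP defines a last follow-up time for children who withdraw early, but the TEAE section does not use it. Protocol Section 15.5 says children who discontinue after dosing are not replaced.

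Late events matter in this study. Under Section 13.1.7, dizziness, hyperesthesia, muscular twitching and paresthesia may become AESIs when they persist or arise later than 72 hours after the dose.

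**Working it through.** The plan has no figure to reproduce here, because the point rests on wording.

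**Step 1: the passages side by side.**

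| Protocol section | Who is covered | Force | How far it runs |
|---|---|---|---|
| 10.3, first paragraph | All who withdraw after dosing | *should* | Day 30 |
| 10.3, second paragraph | AE ongoing at withdrawal | *must* (every effort) | Resolution, or no longer warranted |
| 10.3.1 | AE makes remaining assessments impossible | discontinued; final visit *should* occur | Final visit; Day 30 not mentioned |
| 10.3.2 | Voluntary or investigator withdrawal | *may* | Day 30, optional |
| 9.1 | All dosed subjects | *will* | Day 30 visit |
| 14.1.2 | All AEs | *must* be recorded | Day 30 |
| 14.2.2 | All SAEs and deaths | *must* be reported | Day 30 |

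**Step 2: which events fall in the gap.** An AE ongoing at withdrawal is covered by the second paragraph of 10.3. A new AE is covered by its first paragraph, because Section 12.3 lists AEs to Day 30 among the safety assessments, but only as *should*. For that same new event, 10.3.1 is silent and 10.3.2 is optional. Sections 14.1.2 and 14.2.2 oblige the site to record and report, but they schedule no contact with a child who has left, and the SAE reporting clock starts at discovery. The gap is therefore new events that start after the final evaluation.

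**Step 3: which table rows can be affected.** SAP Section 6.8.4 counts each subject once per reporting level.
- A child with a TEAE before leaving is already in the any-TEAE row, and later unseen events cannot change that.
- For such a child, a first SAE, a first AESI, a higher maximum severity or a new preferred term could still be missed.
- The any-TEAE row can be too low only for a child who left with no TEAE.

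**Step 4: size per affected child.** Each child adds at most one to any row.
- Group 1 arm, Parts 1 and 2 combined: 15 + 15 = 30, and 1/30 = 3.3 percentage points.
- Group 1 arm, if one part were tabulated alone: 1/15 = 6.7 points.
- Group 2: 30 children are split between spine and cardiac columns in numbers the plan does not fix, so one child is worth 3.3 points or more.

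The documents give no withdrawal rate. Assuming one to three leavers in an arm of 30, the ceiling is 1/30 to 3/30, or 3.3 to 10.0 points. It is reached only if every leaver has a missed event in the same row.

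**The case against.** The strongest reply is that the protocol already requires what is needed. Section 10.3 is the parent rule for both subsections, and nothing in 10.3.1 cancels it. The discontinuation in 10.3.1 is confined to a child who cannot continue, and the same section argues from the single dose that other children should stay under assessment. Section 9.1 plans a Day 30 visit for every dosed subject, and recording and reporting are mandatory. For voluntary leavers follow-up depends on consent in any case. The SAP also shows early exit: disposition with reasons (Section 6.2), a TEAE overview row for discontinuation due to a TEAE, and a disposition listing with the date of last visit.

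Much of this stands. It rules out two stronger readings that a reader might infer:

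- *That the protocol stops observing children who leave because of an AE.* The documents do not support this. The AE that made them leave, if still ongoing, must be followed. The *may* sentence is in the section on voluntary or investigator withdrawal, not the one on AE withdrawal. It could still reach some AE-related leavers, since Section 5.3 lets the investigator or sponsor withdraw a subject for safety reasons, but it is not a rule for AE withdrawals as such.
- *That overall TEAE incidence is biased downward by a calculable amount.* Multiplying a withdrawal share, a share of late events and a TEAE rate would need three inputs that the documents do not give. It would also count lost events as lost subjects. For a child who left because of a TEAE, the loss in the any-TEAE row is zero.

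The reply does not remove the conflict itself. *Should*, *may* and *must* cannot all govern the same child. The sentence about continuing while able does not protect the child whom 10.3.1 discontinues for being unable to continue.

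**Conclusion.** The point holds in a narrow form. The force of Day 30 safety follow-up for dosed children who leave is inconsistent across Protocol Sections 9.1, 10.3, 10.3.1, 10.3.2, 14.1.2 and 14.2.2. A site that follows 10.3.1 or 10.3.2 alone could stop looking for new events after the final evaluation, while the endpoint counts events to Day 30 over the full safety population.

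The effect is at most 3.3 points per affected child in a Group 1 arm of 30, assuming Parts 1 and 2 are tabulated together. How many children would be affected cannot be estimated. The sample size and error rates are untouched, since the study is sized on PK and the protocol plans no formal hypothesis test. This is a minor point, worth fixing because the remedy is nearly free and makes the safety data more complete.

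**What to change.** Reconcile Sections 10.3.1 and 10.3.2 with 10.3, 9.1, 14.1.2 and 14.2.2. One sentence used in both subsections would do: AE and SAE collection continues to Day 30, by visit or telephone, for every child who received study drug, including those discontinued for an AE, unless consent for follow-up is withdrawn. The optional wording in 10.3.2 should then go.

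The cost is a short wording change and a few extra contacts. A count in the SAP of subjects whose AE follow-up ended early, by TEAE table column, would help readers. It is optional, because the disposition table and last-visit listing already show who left and when.

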11. TREATMENTS

11.1. Treatments to be Administered

Study Drug

Dosing of EXPAREL for this study will be based on body weight, with a starting dose of 4 mg/kg. This weight-based dosing applies to Part 1 and Part 2 of the study.

The study drug will be administered prior to wound closure. The investigator must document the size of the incision. Each infiltration site should be spaced 1.0 to 1.5 cm apart and approximately 1 to 1.5 mL should be delivered into both deep and superficial areas. Following infiltration, the tissue should visibly expand with minimal leakage.

All eligible subjects will receive a single dose of EXPAREL intraoperatively at the end of surgery via local infiltration into the surgical site. EXPAREL can be administered as is or may be expanded with normal (0.9%) saline to increase the volume up to a final concentration of 0.89 mg/mL (i.e., 1:14 dilution by volume). The total volume of expansion will be dependent on the incision length. Details regarding the expansion of EXPAREL are provided in the Study Drug Infiltration Guide.

Total Volume of Expansion

The investigator must document the total volume used for each surgery.

• EXPAREL 4 mg/kg + normal saline (20–60 mL based on the incision size) = total volume.

For example: If the infiltration sites are 1.5 cm apart, then a 10 cm incision would be 10×2 sides $\times 3$ layers = 60 cm. If there is 1 mL infiltrated every 1.5 cm, the total volume would be 40 mL.

In Part 1, all eligible subjects will receive a single dose of EXPAREL intraoperatively at the end of surgery via local infiltration. EXPAREL can be administered as is or expanded to increase volume up to a final concentration of 0.89 mg/mL (i.e., 1:14 dilution by volume) with normal

saline (0.9% sodium chloride solution). The total volume of expansion will be dependent on the size of the wound.

In Part 2, all eligible subjects randomized to EXPAREL will receive a single dose of EXPAREL intraoperatively at the end of surgery via local infiltration. Dosing will be informed by the results of Part 1 and any recommendations based on the complete safety review.

Subjects randomized to the active control group will receive bupivacaine HCl 2 mg/kg, with a maximum dose of 175 mg.

Postsurgical Pain Management

The use of postsurgical pain medication in cases of insufficient analgesia is permitted according to the institution's standard of care. The investigator must record all pain management medications administered during hospitalization. Avoid additional use of local anesthetics within 96 hours following administration of EXPAREL

11.2. Administration Instructions/Procedures

All injections must be performed with an infiltrative moving needle technique, with frequent aspirations to reduce the chance for accidental intravascular injection. If an aspiration draws blood, the needle must be moved and placed in a different location until the aspiration is negative. The study drug should be infiltrated in small increments into both deep and superficial layers to ensure uniform distribution along the entire length of the surgical wound.

11.2.1. Study Drug Administration Considerations

As there is a potential risk of severe adverse effects associated with the administration of local anesthetics, the study site must be equipped to treat subjects with evidence of cardiac toxicity.

EXPAREL may not be administered to a subject if the vial has been open for more than 4 hours. In order to prevent the study drug from settling, gently inverting and re-inverting the syringe several times prior to administration is recommended. No agents should be admixed with EXPAREL.

11.3. Identity of Investigational Products

11.3.1. Description of EXPAREL

EXPAREL is formulated as a sterile, non-pyrogenic, white to off-white, preservative-free, homogeneous suspension of bupivacaine encapsulated into multivesicular lipid-based particles (the DepoFoam drug delivery system).

Bupivacaine is present at a nominal concentration of 13.3 mg/mL. EXPAREL will be provided in 20 mL, 1.3% (13.3 mg/mL) single-use, clear glass vials.

EXPAREL vials should be stored refrigerated between 2°C and 8°C (36°F to 46°F).

11.3.2. Description of Reference Product

The reference product will be bupivacaine HCl. All information on the drug administered, dose, frequency, and duration will be captured in the electronic case report form (eCRF).

11.3.3. Description of Diluents

Normal saline (0.9% sodium chloride solution) for injection will be used for the expansion of study drug.

11.4. Method of Assigning Subjects to Treatment

11.4.1. Randomization Scheme

Approximately 90 subjects are planned for this study: 45 in Part 1 and 45 in Part 2. The randomization code will be generated by a centralized randomization system, which will also be used to communicate subject randomizations to study sites. All randomized subjects will have both a unique subject identifier and a unique random code identifier. No subject or random code identifiers will be reused once assigned.

11.4.2. Randomization Procedures for Treatment Assignment

Once a subject is identified as being qualified to participate in the study (see Section 10), and is at the study site for surgery, the authorized site staff or designee will obtain a randomization assignment. The subject will be considered randomized into the study once the study treatment assignment is received.

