9. OVERALL STUDY DESIGN AND PLAN

9.1. Overall Study Design and Plan

This is a two-part study to evaluate the PK and safety of EXPAREL in pediatric subjects aged 6 to less than 17 years. Part 1 will evaluate PK and safety in subjects aged 6 to less than 17 years, while Part 2 will assess safety in subjects aged 6 to less than 17 years.

In Part 1, subject enrollment will be conducted in parallel to include the older age group (12 to <17 years old; Group 1) and the younger age group (6 to <12 years old; Group 2).

Subject enrollment for Part 2 (of each group) will commence upon complete enrollment of Part 1 (of that group). In Part 2, subject enrollment will be conducted in parallel to include the older age group (12 to <17 years old; Group 1) and the younger age group (6 to <12 years old; Group 2).

Dosing of EXPAREL will be based on body weight, with a starting dose of 4 mg/kg (maximum 266 mg).

Γ	Surgery Type, Dose, and Number of Subjects [n]			
	Part 1 (PK and Safety)	Part 2 (Safety)		
Group 1 (subjects aged 12 to	Spine Surgery	Spine Surgery		
<17 years)	EXPAREL 4 mg/kg [15] bupivacaine HCl 2 mg/kg [15]	EXPAREL 4 mg/kg [15] bupivacaine HCl 2 mg/kg [15]		
Group 2 (subjects aged 6 to	Spine or Cardiac Surgery	Spine or Cardiac Surgery		
<12 years)	EXPAREL 4 mg/kg [15]	EXPAREL 4 mg/kg [15]		

Part 1 (Pharmacokinetics- PK) - Subjects aged 6 to less than 17 years

Part 1 is a multicenter, randomized, open-label study in 45 subjects aged 6 to less than 17 years of age undergoing spine or cardiac surgeries. There will be two treatment groups: Group 1 will include subjects aged 12 to less than 17 years of age, while Group 2 will include subjects aged 6 to less than 12 years of age.

Part 1, Group 1, is an active-controlled, open-labeled, PK evaluation study in subjects aged 12 to less than 17 years undergoing spine surgery. The active comparator will be bupivacaine HCl. The sample size is a total of 30 subjects (15 subjects per treatment group). Subjects will be randomized 1:1 to receive either a single dose of EXPAREL 4 mg/kg (maximum 266 mg) or bupivacaine HCl 2 mg/kg (not exceeding a maximum bupivacaine HCl dose of 175 mg total) intraoperatively at the end of surgery via local infiltration.

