11.4.3. Replacement of Subjects

Subjects who are withdrawn from the study before receiving study drug may be replaced. Once assigned, subject numbers will not be reused; subjects enrolled to replace those who withdraw will be assigned a unique subject number.

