13.4. Intraoperative Procedures

- Confirm eligibility based on exclusion criterion 9 (i.e., verify that no significant intraoperative events have occurred).
- Prepare study drug.
- Administer study drug at the end of surgery.
- Record start and stop times of study drug administration.
- Record dosage of study drug administered and expansion volume if applicable.
- Record use of intraoperative opioids.
- Record surgery start and stop times.
- Record size of incision.
- Record concomitant medications.
- Record AEs and any treatment(s) for the events.

Refer to Section 13.1.7 for additional procedures in the event a cardiac or neurological AE of special interest or SAE occurs.

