5. ANALYSIS POPULATIONS

The Safety Population will consist of all subjects who underwent the planned surgery and received study treatment. All analyses based on the safety population will be by actual treatment received.

The PK Population will consist of subjects who received study drug and provided at least one quantifiable plasma concentration. All analyses will be by actual treatment received.

All analyses of data collected for exploratory purposes (i.e., data related to pain intensity scores and opioid consumption) will be conducted using the safety population, and analyzed according to the actual treatment received.

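### Protocol 11.4.2 permits open-label Group 1 assignment before the intraoperative check for dosing, so that check can be applied with the arm known

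*Protocol*

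**What the plan says.** **Timing of assignment.** Under Protocol 11.4.2, when a child has qualified (with a pointer to Section 10) and "is at the study site for surgery, the authorized site staff or designee will obtain a randomization assignment", the site may proceed. The same section fixes the moment of randomisation: "The subject will be considered randomized into the study once the study treatment assignment is received".

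**The later check.** After the numbered exclusions, Protocol 10.2 adds that "the subject will be ineligible to receive study drug if he or she meets the following criterion during surgery". The criterion reads "Any clinically significant event or condition uncovered during the surgery (e.g., excessive bleeding, acute sepsis) that might render the subject medically unstable", and it also covers a complicated course after the operation. Protocol 13.4 makes this the first intraoperative step, listed ahead of drug preparation: "Confirm eligibility based on exclusion criterion 9 (i.e., verify that no significant intraoperative events have occurred".

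**Blinding.** Protocol 9.1 states: "Part 1, Group 1, is an active-controlled, open-labeled, PK evaluation study in subjects aged 12 to less than 17 years undergoing spine surgery". Part 2, Group 1 is open-label as well. Each is randomised 1:1 with 15 children per arm.

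**Children not dosed.** Protocol 11.4.3: "Subjects who are withdrawn from the study before receiving study drug may be replaced". SAP Section 5: "The Safety Population will consist of all subjects who underwent the planned surgery and received study treatment". The PK Population also requires dosing. The exploratory pain and opioid analyses use the Safety Population.

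**The concern.** Randomisation protects a comparison only if what happens between assignment and analysis does not depend on the arm. Here a decision that rests on judgement can fall in that gap. Whoever decides whether a bleeding episode is significant enough to withhold study drug may already know which drug it is. If that knowledge shifts the decision even slightly, the treated children in the two arms differ in how complicated their surgery was, and complicated surgery plausibly carries more adverse events and opioid use.

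What is at stake is the Group 1 contrast between EXPAREL and bupivacaine HCl:
- the safety summaries by arm;
- the ANOVA on PK parameters (SAP 6.7.3), shown as a two-sided t-test in Table 14.4-1.1;
- the log-rank p-value for time to first opioid (SAP 6.9.2.1).

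All of these are computed on dosed children, and no analysis set contains everyone randomised.

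**Working it through.** **1. Sequence.** The plan gives no rate or effect size for this point, so the main check is to set the sections side by side.
- 11.4.2 ties assignment to being qualified and at the site.
- 10.2 and 13.4 place the last criterion during surgery.
- Protocol 13.3, 13.4 and Table 1 list no randomisation step, so nothing places assignment after the check.
- 13.4 lists drug preparation after the check, and Table 1 puts it in the operating-room column. No listed step before the check uses the assignment.

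**2. Planned numbers.** EXPAREL: 15 × 4 = 60. Bupivacaine HCl: 15 × 2 = 30. Total 90, matching the plan. Group 1 contributes 30 + 30 = 60, that is 30 per arm over both Parts.

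**3. How often could it happen?** The failure rate q is not given, so it is assumed, with all 60 children assigned before the check. Expected failures = 60q. Chance of at least one = 1 − (1 − q)^60.

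| q (assumed) | Expected | Chance of at least one |
|---|---|---|
| 1% | 0.6 | 45% |
| 2% | 1.2 | 70% |
| 5% | 3 | 95% |
| 10% | 6 | 99.8% |

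**4. How large could the distortion be?** Assumptions, none from the documents:
- the adverse event risk is 20% after uneventful and 60% after complicated surgery;
- one arm withholds its complicated cases and replaces them with uneventful ones;
- the other arm doses k complicated cases;
- arm size n stays fixed, and there is no drug effect.

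The first arm shows 20.0%. The other shows [(n − k) × 0.20 + k × 0.60] / n.

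| k | n = 15 | Difference | n = 30 | Difference |
|---|---|---|---|---|
| 1 | 22.7% | 2.7 points | 21.3% | 1.3 points |
| 2 | 25.3% | 5.3 points | 22.7% | 2.7 points |
| 3 | 28.0% | 8.0 points | 24.0% | 4.0 points |

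The adverse event tables are set up by age group, and Protocol 9.1 pools both Parts for safety, so n = 30 is the relevant column there. The n = 15 column applies to a single Part.

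**5. Harsher assumption.** Suppose every withheld child would have had an event and the replacement is an average child. The arm's rate then falls by k(1 − p)/n. For true rates p of 20% to 60% and k of 1 to 3, this is 1.3 to 8.0 points at n = 30 and 2.7 to 16.0 points at n = 15.

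**6. Against sampling error.** At a 20% risk in both arms, the 95% half-width for a difference is 1.96 × √(2 × 0.20 × 0.80 / n): about 20 points at n = 30 and 29 points at n = 15.

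**The case against.** **The check may already be part of qualifying.** 11.4.2 points to Section 10, which contains the intraoperative criterion. 13.4 calls it an exclusion criterion, and Table 1 marks eligibility confirmation in the operating-room column. This reading is weak. 10.2 words the rule as ineligibility for the drug, not for the study, and 11.4.2 links assignment to presence at the site. What stands is that early assignment is permitted, not mandated.

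**Knowledge of the arm is inferred.** The documents do not say who applies the criterion or that this person knows the arm. The inference rests on the open-label design and the absence of any concealment step.

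**Losses are visible.** A reader might infer that replacement conceals them. It does not. SAP Table 14.1-1.1.1 gives randomised, not treated and treated by arm. Listing 16.2-1.1.1 gives the reason for termination, Listing 16.2-2.1.1 the population flags and Listing 16.2-25.1.1 the failed criteria. A reader might also infer that each arm refills to 15, but 11.4.3 does not say that a replacement enters the same arm.

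**Intraoperative analgesics.** A reader might infer that arm-aware use of opioids or NSAIDs before dosing would go unseen, since opioid totals start at the end of surgery. Intraoperative medications are tabulated by arm in Table 14.1-5.1.1, so an imbalance in which drugs were used would show.

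**Limited consequence.** The protocol plans no formal hypothesis test, efficacy is unpowered and exploratory, and the illustrated shifts are far below sampling error. All of this stands. It limits the severity, but bias does not average out as sampling error does, and the SAP does report between-arm p-values.

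**Conclusion.** The concern holds as a gap in the order of steps. The protocol allows open-label assignment before a post-randomisation exclusion that depends on judgement, and the excluded children drop out of every outcome comparison in Group 1. The existing SAP outputs would reveal this but would not prevent or correct it.

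The size is unknown. The figures of about 1 to 4 points (30 per arm) and 3 to 8 points (15 per arm) rest on assumed risks, withholding in one arm only and fixed arm sizes. They illustrate what is possible and do not estimate what will happen.

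A reader might go further and conclude that the 1:1 randomisation no longer protects the comparison at all. The documents do not support that: early assignment is optional, the assignment is central and protected until its release, and no rate of intraoperative failure is given. The descriptive primary PK objective is little affected, and single-arm Group 2 has no between-treatment comparison to distort. The change is worth making because it is cheap and removes this route by design.

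**What to change.** Amend Protocol 11.4.2 so that, for Group 1 in both Parts, the central system releases the assignment only after the intraoperative check has been recorded, and immediately before study drug is prepared. Add the randomisation step to 13.4 between those two items, and to Table 1 in the operating-room column. The clinical criterion itself stays as written.

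A child who fails the check is then excluded before having an arm, so exclusions after assignment under this criterion become zero by design. The planned 60 Group 1 children (30 per arm) do not change. No new SAP listing is needed, because the disposition and eligibility listings already cover any child randomised but not treated for another reason.

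The cost is protocol wording, a setting in the randomisation system, a brief query during surgery and the logistics of having both drugs available until the arm is known. No patients or clinical procedures are added. The change does not address open-label analgesia or adverse event assessment after dosing.
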